10 MONITORING	
10.1 DATA SAFETY AND MONITORING PLAN (DSMP)	
11 DATA HANDLING AND RECORD KEEPING	
11.1 CRFS / ELECTRONIC DATA RECORD	
11.2 RECORD RETENTION	26
12 ETHICS	27

12.1 IRB	3/FDA	27
	TITUTIONAL REVIEW BOARD (IRB)	
	BJECT INFORMATION AND CONSENT	
	JDY DISCONTINUATION CRITERIA	
	STOPPING RULES FOR SAFETY REASONS	
12.4.2	RULES FOR DISCONTINUATION OF A SUBJECT	28
13 REFE	RENCES	29
	List of Figures	
Figure 1:	Sleep disturbance, pain, and cognitive dysfunction are reciprocally related.	
Figure 2:	Planned study flow diagram based on Consolidated Standards of Reporting Trials (CONSORT)	
Figure 3:	Representative wireless EEG data from a surgical patient	

PROTOCOL SYNOPSIS

Study Title: Caffeine and Neurologic Recovery Following Surgery and General Anesthesia

Study Phase: Phase II

Primary Objective: The objective is to establish feasibility of perioperative caffeine administration in relation to targeted postoperative neurologic outcomes

Study Design: Randomized, triple-blinded, controlled trial with a 1:1 allocation ratio (placebo: caffeine) in a two-arm parallel design

Study Population: Adult (≥18 years old) patients undergoing non-cardiac, non-neurologic, non-major vascular surgery at a tertiary university hospital

Diagnosis and Main Criteria for Inclusion

Each subject must meet the following criteria to be enrolled in this study:

- Adult surgical patients (≥18 years old)
- Non-cardiac, non-neurologic, non-major vascular surgery (i.e., below the diaphragm)

Subjects who meet any of the following criteria will be excluded from study:

- Emergency surgery
- Severe cognitive impairment
- Uncontrolled cardiac arrhythmia history
- Seizure disorder history
- Preoperative opioid use
- Pheochromocytoma
- Caffeine sensitivity/allergy

- Conflicting research study enrollment
- Acute liver failure
- Pregnancy
- Breastfeeding
- Severe audiovisual impairment
- Non-English speaking
- History of diabetes

Test Product; Dose; and Mode of Administration: Caffeine citrate 60 mg/mL (30 mg/mL caffeine). Proposed dose 200 mg caffeine, 40 mL dilution, 60-min IV infusion.

Reference or Placebo Therapy; Dose; and Mode of Administration: 40 mL 5% dextrose in water intravenous infusion over 60 minutes.

Duration of Treatment: 60-minute intravenous infusion

Variables: Postoperative opioid consumption, postoperative pain scores, time to anesthetic emergence, new sleep disturbances, electroencephalographic markers of brain recovery, postoperative cognitive function testing, depression/anxiety/affect scores, and perioperative caffeine use.

Statistical Methods: The analysis will be longitudinal with repeated oral morphine equivalent (OME) measurements i.e. we will analyze multiple points of the OME curve simultaneously. A generalized linear mixed model will be the primary analytic tool with appropriate data-driven choice of the link function. Power calculations reveal >80% power to detect difference by a two-sided t-test with unequal variances.

1 INTRODUCTION

[figure not shown]
1.1 Indication

Pain and cognitive dysfunction remain common and distressing complications after surgery. For example, approximately 75% of patients report moderate/severe pain after surgery, and cognitive dysfunction can persist for months after non-cardiac surgery. Furthermore, these outcomes are interrelated, as pain itself may worsen cognitive function, heading to further overall neurologic impairment. Unfortunately, there are few novel, neurobiologically informed strategies available to pre-emptively address such deleterious outcomes. Although opioids remain a mainstay therapy for managing postoperative pain, opioids can induce cognitive dysfunction, seep disruption, and persistent postoperative use.

1.2 Background and Rationale

Over 300 million surgical procedures are performed each year worldwide, 9 the majority with general anesthesia. Many fundamental questions in the fields of neuroscience and anesthesiology persist, such as the relationship between pain and arousal state perturbations. Evidence suggests a neurobiologic pain-arousal state connection, such that pain, sleep disturbance, and cognitive dysfunction may interact in a synergistic, reciprocating manner (Figure 1).^{4,10-13} In clinical practice, these adverse pain-arousal state interactions are often ineffectively addressed, and surgical patients are particularly vulnerable to entering this refractory cycle given the pain and brain state alterations associated with surgical interventions. In fact, 75% of surgical patients report moderate-to-severe pain after surgery, 1 nearly 50% of patients report sleep disturbances perioperatively, 13 and up to 70% of patients experience cognitive dysfunction after surgery. 14,15 Acute postoperative pain and cognitive dysfunction are also associated with negative outcomes, such as increased hospital length of stay, ¹⁶ persistent opioid use, ⁸ and prolonged cognitive decline. ^{17,18} Opioids remain a mainstay therapy for treating acute surgical pain, but opioids also interfere with sleep architecture^{6,7} and cognitive function, ^{5,19,20} further propagating the deleterious cycle of painarousal state perturbation (Figure 1).

Figure 1: Sleep disturbance, pain, and cognitive dysfunction are reciprocally related.

Preliminary data from our laboratory research group demonstrate that caffeine, a non-selective adenosine receptor antagonist, demonstrates both acute anti-nociceptive properties and protection against postoperative pain in both sleep-deprived and non-sleep-deprived rat models.²¹ In fact, recent systematic reviews found that caffeine provided significant analgesic benefit as part of a multimodal strategy in both surgical²² and non-surgical settings.²³ Caffeine also augments electroencephalographic (EEG) signs of arousal,²⁴ and it has been shown to improve cognitive function in a variety of settings.²⁵ Nonetheless, caffeine is not routinely given perioperatively, and whether caffeine facilitates such neurocognitive arousal after surgery, and how such brain state modulation may impact postoperative pain and opioid requirements, remains unknown.

1.3 Hypothesis

The central hypothesis is that intraoperative caffeine administration will improve opioid consumption, pain, and neuropsychological recovery in patients undergoing surgery.

1.4 Previous Human Experience

Caffeine has been safely used for decades for various clinical indications. Pertinently, caffeine has long track record of safe and effective use in adult surgical and obstetric patients for post-dural puncture/post-operative pain. A targeted literature review is provided below:

Derry et al., 2015 (Cochrane review):²² The objective of this review was to assess the analgesic efficacy and safety of oral ibuprofen plus caffeine for postoperative pain. The number needed to treat for achieving at least 50% maximum pain relief was 2.1 (95% confidence interval, 1.8-2.5) to 2.4 (1.9-3.1). Adverse event rates were similar between placebo and ibuprofen-caffeine groups, and no serious adverse events or withdrawals were reported due to the ibuprofen-caffeine combination.

Basurto Ono et al., 2015 (Cochrane review): ²⁶ The objective of this review was to assess the effectiveness and safety of drugs used for treating post-dural puncture headache. Caffeine was found to be a safe, effective intervention for reducing headache pain in both post-partum and non-obstetric surgery patients. No clinically significant adverse events were reported related to caffeine.

Derry et al., 2014 (Cochrane review): ²³ The objective was to assess relative efficacy of caffeine for acute pain, with surgical patients included as part of a diverse array of clinical settings (i.e., surgical and non-surgical). Significant pain relief was appreciated at doses \geq 100 mg, and no significant adverse events were reported related to caffeine.

Steinbrook et al., 2013:²⁷ The goal of this study was to determine if caffeine sodium benzoate (500 mg) reduced the incidence of postoperative nausea and vomiting (primary outcome). Caffeine was not found to reduce postoperative nausea and vomiting. In fact, more patients randomized to caffeine reported nausea in the PACU (26% vs. 10%,

respectively, p=0.02), though there was no significant difference in vomiting, rescue antiemetics used, or nausea/vomiting over 24 hours. No other adverse events were reported.

Zeger et al., 2012:²⁸ prospective, double-blinded randomized trial (N=16, caffeine arm) conducted in the emergency room for postdural puncture headache. Intravenous caffeine (500-1000 mg) infused over 60 minutes/dose, 80% effective (95% CI 60-100%) for treating headache pain. No adverse events were reported.

Yucel et al., 1999:²⁹ prospective, double-blinded randomized trial (N=30, caffeine arm) conducted with orthopedic surgery patients. 500 mg caffeine-sodium benzoate (250 mg caffeine) infused over 90 minutes, significant improvement in post-spinal headache. No adverse events or side effects were reported.

Weber et al. 1997:³⁰ this prospective, randomized, double-blinded trial examined caffeine efficacy in relation to postoperative headache and recovery time. Caffeine was found to significantly reduce postoperative headache compared to placebo (10% vs. 23%, respectively, p<0.05) in patients at risk for withdrawal symptoms.

Camann et al., 1990:³¹ prospective, double-blinded, randomized trial (N=20, caffeine arm) conducted with postpartum patients. Oral formulation of caffeine (300 mg). Significant improvement noted in spinal headaches. No significant side effects reported with caffeine therapy. 1/20 patients (5%) complained of mild/transient flushing and jitteriness after receiving caffeine, though this was the same proportion in the placebo group (5%).

Jarvis et al., 1986: 32 exploratory study, letter to the editor (N=18) – 500 mg caffeine-sodium benzoate (250 mg caffeine) infused over 60 minutes, second dose if necessary. Significant relief in 14/18 (75%) of patients. No adverse events or significant side effects were reported.

2 STUDY OBJECTIVES AND ENDPOINTS

2.1 Objectives

• A. Measure postoperative pain outcomes in surgical patients receiving caffeine compared to placebo.

As described above, laboratory data from our research team demonstrate that preoperative caffeine administration blunted postoperative pain for up to six postoperative days. ²¹ *We hypothesize that caffeine will improve postoperative pain outcomes*. Cumulative opioid consumption will be measured during the first postoperative week, and validated pain measures (e.g., visual analog scale [VAS], behavioral pain scale [BPS]), will be used to assess postoperative inpatient pain scores.

• B. Compare the clinical effects of caffeine and placebo on neurocognitive recovery from general anesthesia in surgical patients.

Given that caffeine has been found to accelerate anesthetic recovery in laboratory models,³³ reduce low-frequency electroencephalographic (EEG) power,^{24,34,35} and improve cognitive performance across a variety of settings,²⁵ we also hypothesize that caffeine administration will accelerate neurocognitive recovery following surgery and anesthesia. Our team will calculate anesthetic emergence time, characterize EEG patterns during emergence and recovery, and perform cognitive function testing in the postanesthesia care unit (PACU). We will use the validated Trail Making Test (TMT), which provides information on psychomotor speed, visual scanning, mental flexibility, and executive function.³⁶ Such testing will be suitable for the PACU setting..

• C. Compare the clinical effects of caffeine and placebo on neuropsychological recovery after surgery.

Depression has been identified as an independent risk factor for opioid dependence in surgical patients, and caffeine is also associated with reduced risk of depression.³⁷ Thus, we also hypothesize that caffeine will improve mood and reduce signs of depression postoperatively. Symptoms of depression will be assessed using the Hospitalized Anxiety and Depression Scale (HADS),³⁸ and affect will be characterized using the Positive and Negative Affect Schedule (PANAS).³⁹ To differentiate acute cognitive disorders (i.e., hypoactive delirium) from symptoms of depression, the Confusion Assessment Method (CAM) will be used to assess for delirium using our group's previously described methods.^{14,40} We will also administer the Quality of Recovery (QoR) Score in patients post-operatively. This strategy will provide a more comprehensive assessment of the effects of caffeine on postoperative neuropsychological recovery.

2.2 Endpoints

2.2.1 Primary Endpoint

Cumulative opioid consumption (mg) through postoperative day 3 (or discharge, whichever is sooner.

2.2.2 Secondary Endpoint*

- VAS, n, PACU and postoperative days 1-3 (twice daily)
- BPS, n, PACU and postoperative days 1-3 (twice daily)
- Time until anesthetic emergence (min)
- Delirium incidence (%)
- Positive depression screen incidence (%)
- Positive anxiety screen incidence (%)
- Change in affect scores (n)
- Change in Trail Making Test scores (n) from baseline

^{*}Tertiary assessments are listed in section 7.2

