Inclusion criteria: Adult (≥18 years old) patients undergoing non-cardiac, non-neurologic, non-major vascular surgery (i.e., below the diaphragm).

Exclusion criteria: Emergency surgery, cognitive impairment precluding capacity for informed consent, uncontrolled cardiac arrhythmias, seizure disorders, intolerance or allergy to caffeine, history of diabetes, preoperative opioid use, pheochromocytoma, acute liver failure, enrolled in conflicting research study, pregnancy, breastfeeding, severe visual or auditory impairment (may hinder cognitive function testing), and patients unable to speak English.

Perioperative and anesthetic procedures: Patients will be consented and enrolled at preoperative clinic locations, where a medical and psychiatric history will be taken and baseline assessments will be administered (described further below). After enrollment, patients will also complete a caffeine intake survey to quantify baseline caffeine consumption. On the day of surgery, baseline cognitive function testing (TMT) will take place in the preoperative holding area. Subsequently a 16-channel wireless EEG system (Cognionics, Inc.) will be applied to the scalp for continuous monitoring during surgery and the perioperative period. Once in the operating room, anesthetic induction and maintenance will proceed as deemed clinically appropriate by the anesthesia team. At the beginning of surgical closure, the study drug will be given via intravenous infusion over 60 minutes (placebo vs. caffeine, 200 mg) in a triple-blinded fashion: the anesthetic team, research staff, and patient will all be blinded to the intervention. Infusion of this dose over a 60-minute period has been safely described, without significant side effects or adverse events noted.^{28,32} A member of the research team will remain in the operating room to monitor drug infusion and collect data regarding timing of anesthetic discontinuation and emergence; this will aid methodological rigor and data validation for the study. The EEG sensors will remain in place during the operation and emergence from anesthesia; they will then be removed shortly after PACU arrival. One hour after the caffeine infusion finishes, pain and cognitive function measures will be assessed.

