Neurocognitive assessments: Time from surgical closure to anesthetic emergence will be calculated by the study team. (minutes). The Trail Making Test will be used to assess perioperative cognitive function. The TMT is a validated, reliable test that assesses four cognitive domains relevant to the perioperative setting: processing speed, attention, visual scanning, executive function, and working memory. The TMT is administered in a standardized fashion using paper and pencil and takes approximately 5 minutes to complete. This is a feasible strategy in the perioperative setting to obtain comprehensive cognitive function data (e.g., attention, executive function) in a relatively short period of time, and normalized population data are available for comparisons. The test will be administered preoperatively and one hour after the caffeine infusion has completed in conjunction with pain assessments. Changes (n) in standardized scores from baseline will be calculated, and final standardized scores (n) will also be calculated and reported in the event that baseline scores are unable to be obtained (given the time-constraints present in the preoperative setting, it might not be possible to achieve baseline cognitive function scores in all patients).

Neuropsychological assessments: The Hospital Anxiety and Depression Scale (HADS)³⁸ will be used to assess for active depression and anxiety symptoms in each group. These assessments will take place at baseline and after the last inpatient assessment on postoperative day 3. Scores ≥8 for the anxiety (HADS-A) and depression (HADS-D) subscales will be considered positive screens.⁵¹ The Positive and Negative Affect Schedule

(PANAS)³⁹ will be used to characterize mood and affect at the same time points as depression and anxiety screening (baseline and postoperative day 3). The *Confusion Assessment Method (CAM)* will be used to assess for delirium throughout the first three postoperative days using previously described methods.^{14,40} Lastly, a follow-up health and well-being survey will be sent to participants thirty days after surgery. This survey will include the Veterans RAND 12 Item Health Survey (VR-12, continuous measure).⁵² Presence of persistent opioid use (yes/no, binary) will also be asked in this thirty-day survey.

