6 STUDY PROCEDURES

6.1 Screening Visit

For initial screening visits, patients will be seen during preoperative clinic visits. The study coordinator will review the study details with potential participants, and informed consent will be obtained after confirming eligibility criteria are met. Depending on when a preoperative clinic visit is scheduled in relation to surgery, the timeframe from enrollment to drug administration may vary significantly (days-to-weeks). The goal will be to recruit patients whose surgeries are scheduled for the morning, so as to minimize the likelihood of administering caffeine late in the afternoon. See "Schedule of Activities" for full list of procedures that will occur at this visit and all subsequent visits. Assessments, testing, and measures are described in detail in the above "Study Design" section.

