6.2.3 Follow-up (Postoperative Days 4-7)

During this time, opioid consumption and caffeine intake assessments will be obtained over the telephone. Adverse events will continue to be monitored.

SCHEDULE OF ACTIVITIES

	Screen	Visit 1 Day 1	Visit 2 Day 2	Visit 3 Day 3	Visit 4 Day 4	Phone call Days 5-7	Day 30
Protocol Activity		Day of Surgery	POD1	POD2	POD3	POD4-7	
Visit (POD1-3) /Phone call (POD4-7)	-	X	X	X	X	X	
Informed consent	X						
Medical history	X						
Vitals*	X	X	X	X	X		
Depression, Anxiety, and Affect Scales	X			X			
Serum pregnancy test		X					
Randomization		X					
Treatment with study agent		X					
Opioid use assessments		X	X	X	X	X	
Cognitive function testing	X	X^{\dagger}					
Pain/sleep assessments [‡]	X	X	X	X	X		
Caffeine intake assessment	X		X	X	X	X	
EEG assessments		X			·		
Adverse event assessment	_	X	X	X	X	X	
Health and well-being survey							X

^{*} Vitals will be recorded per clinical protocol on each respective ward/ICU. †Second cognitive function testing session will occur in the postanesthesia care unit ‡Pain and sleep assessments will occur and twice daily (morning and afternoon) from POD1-3; the RCSQ in particular will be administered on Day 1, preoperatively. Pain assessments will also be taken once in the postanesthesia care unit prior to the cognitive function assessment. POD = postoperative day, TMT = trail making test, EEG = electroencephalogram

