9.2.4 Analysis of Secondary Endpoints

For secondary endpoints, continuous data will be analyzed using Student's t-test or Mann-Whitney U test, as appropriate. Categorical data will be analyzed using chi-squared or Fisher's Exact tests, as appropriate. Modeling will be performed similar to the above primary endpoint description if appropriate.

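### Change in PANAS affect is compared without adjusting for the baseline score, which gives up precision that data already collected could supply

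*Combined protocol and SAP*

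**What the plan says.** Sections 2.2.2 and 7.2 both list change in affect among the secondary outcomes; section 2.2.2 has "Change in affect scores (n"). Section 3 names the instrument, the PANAS, which "will be used to characterize mood and affect at the same time points as depression and anxiety screening (baseline and postoperative day 3").

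The baseline comes from the clinic visit. Section 3 states: "Patients will be consented and enrolled at preoperative clinic locations, where a medical and psychiatric history will be taken and baseline assessments will be administered". In the schedule of activities, the row "Depression, Anxiety, and Affect Scales" is marked under screening and not on the day of surgery. Section 6.1 adds that "the timeframe from enrollment to drug administration may vary significantly (days-to-weeks").

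For the analysis, section 9.2.4 says "continuous data will be analyzed using Student's t-test or Mann-Whitney U test, as appropriate". It then allows a second route: "Modeling will be performed similar to the above primary endpoint description if appropriate". The primary-endpoint model in section 9.2.3 has Group, Time and Group-by-Time terms and a random subject intercept, with baseline as one level of Time. Its extended versions add demographic variables and then intraoperative factors. Section 9.2.2 brings into multivariable models any measure whose standardized difference between groups exceeds 0.1. Nowhere is baseline PANAS named in advance as a covariate.

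**The concern.** Subtracting baseline fixes its coefficient at 1. Regression lets the data choose the coefficient, and the best choice is smaller than 1 when baseline predicts follow-up only partly. Fixing it at 1 puts baseline noise into the comparison. The weaker the correlation, the greater the cost, and below a threshold the change score is noisier than the follow-up score alone.

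A long and variable gap between the clinic visit and surgery could weaken that correlation, which is why the question arises for affect in particular. Objective C predicts better mood with caffeine. Its other outcomes in the section 2.2.2 list (delirium, positive depression screen, positive anxiety screen) are incidences, so affect is the only continuous one. With about 30 patients per arm, lost precision on it is not trivial.

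**Working it through.** **Inputs from the documents.** 30 per arm (Figure 2 in section 3; total 60 in section 9.1); two-sided test (section 9.1); one baseline and one follow-up PANAS (section 3).

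**Assumptions, not in the documents.** 5% significance level; equal baseline and follow-up SDs unless stated; correlation r shown over a range; true effect of 0.6 follow-up SDs.

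**The plan's own power figure.** Section 9.1 gives 83% for the opioid endpoint; none is given for PANAS. With a difference of 6.5 − 0.7 = 5.8, SDs of 3 and 10 and 30 per arm, the standard error is √(9/30 + 100/30) = 1.906. The noncentrality is 5.8/1.906 = 3.04 on 34.2 df, and Welch power is 84.0%. That is close to the stated 83%, so 30 per arm and a two-sided 5% level are reasonable settings here.

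**Variances per patient, follow-up variance set to 1, equal SDs.**
- Change: 2(1 − r)
- Follow-up only: 1
- Baseline-adjusted (ANCOVA): 1 − r²
- Ratio of ANCOVA to change: (1 − r²)/[2(1 − r)] = (1 + r)/2

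**Power.** Noncentral t with noncentrality 0.6 × √(15/variance), about 58 df:

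| r | Variance: change / follow-up / ANCOVA | ANCOVA saving against change | Power: change / follow-up / ANCOVA |
|---|---|---|---|
| 0.3 | 1.40 / 1.00 / 0.91 | 35% | 49% / 63% / 67% |
| 0.5 | 1.00 / 1.00 / 0.75 | 25% | 63% / 63% / 75% |
| 0.7 | 0.60 / 1.00 / 0.51 | 15% | 84% / 63% / 89% |

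To match ANCOVA on 60 patients, a change-score test needs 60 × 2/(1 + r) patients: 92, 80 and 71 in these three rows. Simulation at 30 per arm (20,000 runs), with the adjustment slope estimated, gave ANCOVA variances of 0.93, 0.77 and 0.52. Estimating the slope therefore costs about 2% of variance.

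**Unequal SDs.** The change-score variance is SD_pre² + SD_post² − 2r·SD_pre·SD_post. It exceeds SD_post² only when r < SD_pre/(2·SD_post). That threshold is 0.5 with equal SDs, 0.40 if the follow-up SD is 1.25 times the baseline SD, and about 0.62 if it is 0.8 times. Subtracting the ANCOVA variance SD_post²(1 − r²) from the change-score variance leaves (SD_pre − r·SD_post)², which is never negative. Apart from the small cost of estimating the slope, adjustment is therefore never less precise than change.

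**The optional modelling route.** With two time points and free Group and Time terms, Group-by-Time is the difference in mean change. In one simulated data set of 60 patients, the mixed model and the change-score t-test both gave 0.697 (SE 0.272); ANCOVA on the same data had SE 0.209.

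**The imbalance rule.** With 30 per arm, a standardized difference has chance SD of about √(2/30) = 0.258. It exceeds 0.1 in absolute value with probability 2[1 − Φ(0.1/0.258)], about 70%. Baseline affect would often qualify, but only if it counts as a relevant predictor, only if a multivariable model is fitted, and only after the imbalance has been seen.

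**Does the endpoint need to change?** No. Regressing change on arm and baseline gives the same arm estimate and standard error as regressing follow-up on arm and baseline. Only the baseline coefficient differs, by exactly 1.

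**The case against.** A two-group test on change is valid and unbiased in a randomized trial. Affect is one of eight listed secondary endpoints in a Phase II trial whose synopsis states a feasibility objective, and it was not powered. The preference for ANCOVA over change scores is general rather than peculiar to this plan. If r is high the plan does well: at r = 0.7 the change score has 84% power against 63% for follow-up only, and trails ANCOVA by 5 points. All of this stands, and it limits the weight of the point.

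It may also be said that sections 9.2.4 and 9.2.2 already leave room for adjustment. That stands only in part. The optional model reproduces the change contrast, and the imbalance rule depends on the data, so neither commits the analysis to baseline PANAS.

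A reader might infer from section 6.1 that the clinic baseline is stale and that subtracting it will do worse than ignoring it. The documents do not support that. They describe a variable gap and give no PANAS correlation or SDs. A correlation below the threshold is possible but not shown.

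**Conclusion.** The planned comparison is sound but not the most precise one available. The loss does not depend on r being low. With equal SDs it is present at every r below 1, and ANCOVA removes 15% to 35% of the change-score variance for r between 0.7 and 0.3. In power, that is 5 to 18 points at 30 per arm and an assumed 0.6 SD effect. These sizes rest on the assumed r, effect, significance level and equal SDs. Whether the change score would also be worse than follow-up alone cannot be settled from the documents. Nothing here implies bias or touches the primary analysis. It is a modest, worthwhile improvement to one secondary endpoint.

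**What to change.** Keep the endpoint in sections 2.2.2 and 7.2 as change in affect. Add to section 9.2.4 that change in positive affect and change in negative affect are analysed separately, each by linear regression on treatment arm with its own baseline score as a covariate, plus age and gender, the stratification factors named in section 3. State that baseline is included whatever imbalance is observed. Unadjusted change can still be reported descriptively.

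The cost is a few degrees of freedom and a short wording amendment, which section 12.2 sends to the IRB for approval. No new data are needed.
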